14.1.7 Baseline documentation of target and non-target lesions

For the evaluation of lesions at baseline and throughout the study, the lesions are classified at baseline as either target or non-target lesions:

- **Target lesions:** All measurable lesions (nodal and non-nodal) up to a maximum of five lesions in total (and a maximum of two lesions per organ), representative of all involved organs should be identified as target lesions and recorded and measured at baseline. Target lesions should be selected on the basis of their size (lesions with the longest diameter) and their suitability for accurate repeated measurements (either by imaging techniques or clinically). Each target lesion must be uniquely and sequentially numbered on the CRF (even if it resides in the same organ).

Minimum target lesion size at baseline

- **Non-nodal target:** Non-nodal target lesions identified by methods for which slice thickness is not applicable (e.g. clinical examination, photography) should be at least 10 mm in longest diameter. See [Section 14.1.4](#).
- **Nodal target:** See [Section 14.1.4](#).

A sum of diameters (long axis for non-nodal lesions, short axis for nodal) for all target lesions will be calculated and reported as the baseline sum of diameters (SOD). The baseline sum of diameters will be used as reference by which to characterize the objective tumor response. Each target lesion identified at baseline must be followed at each subsequent evaluation and documented on eCRF.

- **Non-target lesions:** All other lesions are considered non-target lesions, i.e. lesions not fulfilling the criteria for target lesions at baseline. Presence or absence or worsening of non-target lesions should be assessed throughout the study; measurements of these lesions are not required. Multiple non-target lesions involved in the same organ can be assessed as a group and recorded as a single item (i.e. multiple liver metastases). Each non-target lesion identified at baseline must be followed at each subsequent evaluation and documented on eCRF.

14.1.8 Follow-up evaluation of target and non-target lesions

To assess tumor response, the sum of diameters for all target lesions will be calculated (at baseline and throughout the study). At each assessment response is evaluated first separately for the target (Table 14-1) and non-target lesions (Table 14-2) identified at baseline. These evaluations are then used to calculate the overall lesion response considering both the target and non-target lesions together (Table 14-3) as well as the presence or absence of new lesions.

14.1.9 Follow-up and recording of lesions

At each visit and for each lesion the actual date of the scan or procedure which was used for the evaluation of each specific lesion should be recorded. This applies to target and non-target lesions as well as new lesions that are detected. At the assessment visit all of the separate lesion evaluation data are examined by the investigator in order to derive the overall visit response. Therefore all such data applicable to a particular visit should be associated with the same assessment number.

14.1.10 Non-nodal lesions

Following treatment, lesions may have longest diameter measurements smaller than the image reconstruction interval. Lesions smaller than twice the reconstruction interval are subject to substantial “partial volume” effects (i.e., size may be underestimated because of the distance of the cut from the longest diameter; such lesions may appear to have responded or progressed on subsequent examinations, when, in fact, they remain the same size).

If the lesion has completely disappeared, the lesion size should be reported as 0 mm.

Measurements of non-nodal target lesions that become 5 mm or less in longest diameter are likely to be non-reproducible. Therefore, it is recommended to report a default value of 5 mm, instead of the actual measurement. This default value is derived from the 5 mm CT slice thickness (but should not be changed with varying CT slice thickness). Actual measurement should be given for all lesions larger than 5 mm in longest diameter irrespective of slice thickness/reconstruction interval.

In other cases where the lesion cannot be reliably measured for reasons other than its size (e.g., borders of the lesion are confounded by neighboring anatomical structures), no measurement should be entered and the lesion cannot be evaluated.

14.1.11 Nodal lesions

A nodal lesion less than 10 mm in size by short axis is considered normal. Lymph nodes are not expected to disappear completely, so a “non-zero size” will always persist.

Measurements of nodal target lesions that become 5 mm or less in short axis are likely to be non-reproducible. Therefore, it is recommended to report a default value of 5 mm, instead of the actual measurement. This default value is derived from the 5 mm CT slice thickness (but should not be changed with varying CT slice thickness). Actual measurement should be given for all lesions larger than 5 mm in short axis irrespective of slice thickness/reconstruction interval.

However, once a target nodal lesion shrinks to less than 10 mm in its short axis, it will be considered normal for response purpose determination. The lymph node measurements will continue to be recorded to allow the values to be included in the sum of diameters for target lesions, which may be required subsequently for response determination.

14.1.12 Determination of target lesion response

Table 14-1 Response criteria for target lesions

Response Criteria	Evaluation of target lesions
Complete Response (CR):	Disappearance of all non-nodal target lesions. In addition, any pathological lymph nodes assigned as target lesions must have a reduction in short axis to < 10 mm ¹
Partial Response (PR):	At least a 30% decrease in the sum of diameter of all target lesions, taking as reference the baseline sum of diameters.
Progressive Disease (PD):	At least a 20% increase in the sum of diameter of all measured target lesions, taking as reference the smallest sum of diameter of all target lesions recorded at or after baseline. In addition to the relative increase of 20%, the sum must also demonstrate an absolute increase of at least 5 mm ² .
Stable Disease (SD):	Neither sufficient shrinkage to qualify for PR or CR nor an increase in lesions which would qualify for PD.
Unknown (UNK)	Progression has not been documented and one or more target lesions have not been assessed or have been assessed using a different method than baseline. ³

¹. SOD for CR may not be zero when nodal lesions are part of target lesions

². Following an initial CR, a PD cannot be assigned if all non-nodal target lesions are still not present and all nodal lesions are <10 mm in size. In this case, the target lesion response is CR

³. Methodology change See [Section 14.1.6](#).

Notes on target lesion response

Reappearance of lesions: If the lesion appears at the same anatomical location where a target lesion had previously disappeared, it is advised that the time point of lesion disappearance (i.e., the “0 mm” recording) be re-evaluated to make sure that the lesion was not actually present and/or not visualized for technical reasons in this previous assessment. If it is not possible to change the 0 value, then the investigator/radiologist has to decide between the following three possibilities:

- The lesion is a new lesion, in which case the overall tumor assessment will be considered as progressive disease
- The lesion is clearly a reappearance of a previously disappeared lesion, in which case the size of the lesion has to be entered in the CRF and the tumor assessment will remain based on the sum of tumor measurements as presented in [Table 14-1](#) above (i.e., a PD will be determined if there is at least 20% increase in the sum of diameters of **all** measured target lesions, taking as reference the smallest sum of diameters of all target lesions recorded at or after baseline with at least 5 mm increase in the absolute sum of the diameters). Proper documentation should be available to support this decision. This applies to patients who have not achieved target response of CR. For patients who have achieved CR, please refer to last bullet in this section.
- For those patients who have only one target lesion at baseline, the reappearance of the target lesion which disappeared previously, even if still small, is considered a PD.

- **Missing measurements:** In cases where measurements are missing for one or more target lesions it is sometimes still possible to assign PD based on the measurements of the remaining lesions. For example, if the sum of diameters for 5 target lesions at baseline is 100 mm at baseline and the sum of diameters for 3 of those lesions at a post-baseline visit is 140 mm (with data for 2 other lesions missing) then a PD should be assigned. However, in other cases where a PD cannot definitely be attributed, the target lesion response would be UNK.
- **Nodal lesion decrease to normal size:** When nodal disease is included in the sum of target lesions and the nodes decrease to “normal” size they should still have a measurement recorded on scans. This measurement should be reported even when the nodes are normal in order not to overstate progression should it be based on increase in the size of nodes.
- **Lesions split:** In some circumstances, disease that is measurable as a target lesion at baseline and appears to be one mass can split to become two or more smaller sub-lesions. When this occurs, the diameters (long axis - non-nodal lesion, short axis - nodal lesions) of the two split lesions should be added together and the sum recorded in the diameter field on the case report form under the original lesion number. This value will be included in the sum of diameters when deriving target lesion response. The individual split lesions will not be considered as new lesions, and will not automatically trigger a PD designation.
- **Lesions coalesced:** Conversely, it is also possible that two or more lesions which were distinctly separate at baseline become confluent at subsequent visits. When this occurs a plane between the original lesions may be maintained that would aid in obtaining diameter measurements of each individual lesion. If the lesions have truly coalesced such that they are no longer separable, the maximal diameters (long axis - non-nodal lesion, short axis - nodal lesions) of the “merged lesion” should be used when calculating the sum of diameters for target lesions. On the case report form, the diameter of the “merged lesion” should be recorded for the size of one of the original lesions while a size of “0”mm should be entered for the remaining lesion numbers which have coalesced.
- The **measurements for nodal lesions**, even if less than 10 mm in size, will contribute to the calculation of target lesion response in the usual way with slight modifications.
 - Since lesions less than 10 mm are considered normal, a CR for target lesion response should be assigned when all nodal target lesions shrink to less than 10 mm and all non-nodal target lesions have disappeared.
 - Once a CR target lesion response has been assigned a CR will continue to be appropriate (in the absence of missing data) until progression of target lesions.
 - Following a CR, a PD can subsequently only be assigned for target lesion response if either a non-nodal target lesion “reappears” or if any single nodal lesion is at least 10 mm and there is at least 20% increase in sum of the diameters of all nodal target lesions relative to nadir with at least 5 mm increase in the absolute sum of the diameters.

14.1.13 Determination of non-target lesion response

Table 14-2 Response criteria for non-target lesions

Response Criteria	Evaluation of non-target lesions
Complete Response (CR):	Disappearance of all non-target lesions. In addition, all lymph nodes assigned a non-target lesions must be non-pathological in size (< 10 mm short axis)
Progressive Disease (PD):	Unequivocal progression of existing non-target lesions. ¹
Non-CR/Non-PD:	Neither CR nor PD
Unknown (UNK)	Progression has not been documented and one or more non-target lesions have not been assessed or have been assessed using a different method than baseline.

¹. Although a clear progression of non-target lesions only is exceptional, in such circumstances, the opinion of the treating physician does prevail and the progression status should be confirmed later on by the review panel (or study chair).

Notes on non-target lesion response

- The response for non-target lesions is **CR** only if all non-target non-nodal lesions which were evaluated at baseline are now all absent and with all non-target nodal lesions returned to normal size (i.e. < 10 mm). If any of the non-target lesions are still present, or there are any abnormal nodal lesions (i.e. ≥ 10 mm) the response can only be '**Non-CR/Non-PD**' unless any of the lesions was not assessed (in which case response is **UNK**) or there is unequivocal progression of the non-target lesions (in which case response is **PD**).
- Unequivocal progression: To achieve "unequivocal progression" on the basis of non-target disease there must be an overall level of substantial worsening in non-target disease such that, even in presence of CR, PR or SD in target disease, the overall tumor burden has increased sufficiently to merit discontinuation of therapy. A modest "increase" in the size of one or more non-target lesions is usually not sufficient to qualify for unequivocal progression status. The designation of overall progression solely on the basis of change in non-target disease in the face of CR, PR or SD of target disease is therefore expected to be rare. In order for a PD to be assigned on the basis of non-target lesions, the increase in the extent of the disease must be substantial even in cases where there is no measurable disease at baseline. If there is unequivocal progression of non-target lesion(s), then at least one of the non-target lesions must be assigned a status of "Worsened". Where possible, similar rules to those described in [Section 14.1.12](#) for assigning PD following a CR for the non-target lesion response in the presence of non-target lesions nodal lesions should be applied.

14.1.14 New lesions

The appearance of a new lesion is always associated with Progressive Disease (PD) and has to be recorded as a new lesion in the New Lesion CRF page.

- If a new lesion is **equivocal**, for example because of its small size, continued therapy and follow-up evaluation will clarify if it represents truly new disease. If repeat scans confirm there is definitely a new lesion, then progression should be declared using the date of the first observation of the lesion.

- If new disease is observed in a region which was **not scanned at baseline** or where the particular baseline scan is not available for some reason, then this should be considered as a PD. The one exception to this is when there are no baseline scans at all available for a patient in which case the response should be UNK, as for any of this patient's assessment (see [Section 14.1.15](#)).
- A **lymph node is considered as a “new lesion”** and, therefore, indicative of progressive disease if the short axis increases in size to ≥ 10 mm for the first time in the study plus 5 mm absolute increase.
FDG-PET: can complement CT scans in assessing progression (particularly possible for ‘new’ disease). See [Section 14.1.6](#).

14.1.15 Evaluation of overall lesion response

The evaluation of overall lesion response at each assessment is a composite of the target lesion response, non-target lesion response and presence of new lesions as shown below in Table 14-3.

Table 14-3 Overall lesion response at each assessment

Target lesions	Non-target lesions	New Lesions	Overall lesion response
CR	CR	No	CR ¹
CR	Non-CR/Non-PD ³	No	PR
CR, PR, SD	UNK	No	UNK
PR	Non-PD and not UNK	No	PR ¹
SD	Non-PD and not UNK	No	SD ^{1, 2}
UNK	Non-PD or UNK	No	UNK ¹
PD	Any	Yes or No	PD
Any	PD	Yes or No	PD
Any	Any	Yes	PD

¹. This overall lesion response also applies when there are no non-target lesions identified at baseline.

². Once confirmed PR was achieved, all these assessments are considered PR.

³. As defined in [Section 14.1.8](#).

If there are no baseline scans available at all, then the overall lesion response at each assessment should be considered Unknown (UNK).

If the evaluation of any of the target or non-target lesions identified at baseline could not be made during follow-up, the overall status must be ‘unknown’ unless progression was seen.

In some circumstances it may be difficult to distinguish residual disease from normal tissue. When the evaluation of complete response depends on this determination, it is recommended that the residual lesion be investigated (fine needle aspirate/biopsy) to confirm the CR.

14.1.16 Efficacy definitions

The following definitions primarily relate to patients who have measurable disease at baseline. [Section 14.1.26](#) outlines the special considerations that need to be given to patients with no measurable disease at baseline in order to apply the same concepts.

14.1.17 Best overall response

The best overall response is the best response recorded from the start of the treatment until disease progression/recurrence (taking as reference for PD the smallest measurements recorded since the treatment started). In general, the patient's best response assignment will depend on the achievement of both measurement and confirmation criteria.

The best overall response will usually be determined from response assessments undertaken while on treatment. However, if any assessments occur after treatment withdrawal the protocol should specifically describe if these will be included in the determination of best overall response and/or whether these additional assessments will be required for sensitivity or supportive analyses. As a default, any assessments taken more than 30 days after the last dose of study treatment will not be included in the best overall response derivation. If any alternative cancer therapy is taken while on study any subsequent assessments would ordinarily be excluded from the best overall response determination. If response assessments taken after withdrawal from study treatment and/or alternative therapy are to be included in the main endpoint determination, then this should be described and justified in the protocol.

Where a study requires confirmation of response (PR or CR), changes in tumor measurements must be confirmed by repeat assessments that should be performed not less than 4 weeks after the criteria for response are first met.

Longer intervals may also be appropriate. However, this must be clearly stated in the protocol. The main goal of confirmation of objective response is to avoid overestimating the response rate observed. In cases where confirmation of response is not feasible, it should be made clear when reporting the outcome of such studies that the responses are not confirmed.

- -For non-randomized trials where response is the primary endpoint, confirmation is needed.
- -For trials intended to support accelerated approval, confirmation is needed
- For all other trials, confirmation of response may be considered optional.

The best overall response for each patient is determined from the sequence of overall (lesion) responses according to the following rules:

- CR = at least two determinations of CR at least 4 weeks apart before progression where confirmation required or one determination of CR prior to progression where confirmation not required
- PR = at least two determinations of PR or better at least 4 weeks apart before progression (and not qualifying for a CR) where confirmation required or one determination of PR prior to progression where confirmation not required
- SD = at least one SD assessment (or better) > 6 weeks after randomization/start of treatment (and not qualifying for CR or PR).
- PD = progression ≤ 12 weeks after randomization/ start of treatment (and not qualifying for CR, PR or SD).
- UNK = all other cases (i.e. not qualifying for confirmed CR or PR and without SD after more than 6 weeks or early progression within the first 12 weeks)

Overall lesion responses of CR must stay the same until progression sets in, with the exception of a UNK status. A patient who had a CR cannot subsequently have a lower status other than a PD, e.g. PR or SD, as this would imply a progression based on one or more lesions reappearing, in which case the status would become a PD.

Once an overall lesion response of PR is observed (which may have to be a confirmed PR depending on the study) this assignment must stay the same or improve over time until progression sets in, with the exception of an UNK status. However, in studies where confirmation of response is required, if a patient has a single PR ($\geq 30\%$ reduction of tumor burden compared to baseline) at one assessment, followed by a $<30\%$ reduction from baseline at the next assessment (but not $\geq 20\%$ increase from previous smallest sum), the objective status at that assessment should be SD. Once a confirmed PR was seen, the overall lesion response should be considered PR (or UNK) until progression is documented or the lesions totally disappear in which case a CR assignment is applicable. In studies where confirmation of response is not required after a single PR the overall lesion response should still be considered PR (or UNK) until progression is documented or the lesion totally disappears in which case a CR assignment is applicable.

Example: In a case where confirmation of response is required the sum of lesion diameters is 200 mm at baseline and then 140 mm - 150 mm - 140 mm - 160 mm - 160 mm at the subsequent visits. Assuming that non-target lesions did not progress, the overall lesion response would be PR - SD - PR - PR - PR. The second assessment with 140 mm confirms the PR for this patient. All subsequent assessments are considered PR even if tumor measurements decrease only by 20% compared to baseline (200 mm to 160 mm) at the following assessments.

If the patient progressed but continues study treatment, further assessments are not considered for the determination of best overall response.

Note: these cases may be described as a separate finding in the CSR but not included in the overall response or disease control rates.

The best overall response for a patient is always calculated, based on the sequence of overall lesion responses. However, the overall lesion response at a given assessment may be provided from different sources:

- Investigator overall lesion response
- Central Blinded Review overall lesion response
- Novartis calculated overall lesion response (based on measurements from either Investigator or Central Review)

The primary analysis of the best overall response will be based on the sequence of investigator/central blinded review/calculated (investigator)/calculated (central) overall lesion responses.

Based on the patients' best overall response during the study, the following rates are then calculated:

Overall response rate (ORR) is the proportion of patients with a best overall response of CR or PR. This is also referred to as 'Objective response rate' in some protocols or publications.

Disease control rate (DCR) is the proportion of patients with a best overall response of CR or PR or SD.

Another approach is to summarize the progression rate at a certain time point after baseline. In this case, the following definition is used:

Early progression rate (EPR) is the proportion of patients with progressive disease within 8 weeks of the start of treatment.

The protocol should define populations for which these will be calculated. The timepoint for EPR is study specific. EPR is used for the multinomial designs of [Dent and Zee \(2001\)](#) and counts all patients who at the specified assessment (in this example the assessment would be at 8 weeks \pm window) do not have an overall lesion response of SD, PR or CR. Patients with an unknown (UNK) assessment at that time point and no PD before, will not be counted as early progressors in the analysis but may be included in the denominator of the EPR rate, depending on the analysis population used. Similarly when examining overall response and disease control, patients with a best overall response assessment of unknown (UNK) will not be regarded as “responders” but may be included in the denominator for ORR and DCR calculation depending on the analysis population (e.g. populations based on an ITT approach).

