7.1 Study flow and visit schedule

[Table 7-1](#) lists all of the assessments and indicates with an “X”, the visits when they are performed. All data obtained from these assessments must be supported in the patient’s source documentation.

No CRF will be used as a source document.

The table indicates which assessments produce data to be entered into the clinical database (D) or remain in source documents only (S) (“Category” column). Tests, procedures and visits should occur on schedule whenever possible. However, tests, procedures, and visits that occur outside the prescribed allowable windows indicated in [Table 7-1](#) will not constitute protocol deviations.

Table 7-1 Visit evaluation schedule

	Category	Protocol Section 7.2	Screening/ Baseline (-28~0day)	Visit 1 (day1)	Visit 2 (day28±2d)	Visit 3 (week 12±1wk)	Subsequent visits (every 12wk±1wk)	End of study treatment (EOT)	30-day Safety Follow-up	Survival follow up (every 6 months)
Obtain Informed Consent	D		X							
Patient history	D		X							
Demography	D		X							
Inclusion/exclusion criteria	D		X							
Relevant medical history/current medical conditions	D		X							
Diagnosis of cancer	D		X							
Prior/concomitant medications	D		X	X	X	X	X	X		
Physical examination	S	7.2.2.1	X	X	X	X	X	X		
Vital signs	D	7.2.2.2	X	X	X	X	X	X		
Height/Weight	D	7.2.2.3	X							
Laboratory assessments		7.2.2.4								
Hematology ^a	D	7.2.2.4.1	X	X	X	X	X	X		
Liver function tests ^b	D	7.2.2.4.2	X		X	X	X	X		
Coagulation	S	7.2.2.4.3	X		X	X	X	X		
Other laboratory test ^c	S	7.2.2.4.6		Only to be done if clinically indicated						
Urinalysis ^c	S	7.2.2.4.4	X	Only to be done if clinically indicated						
Pregnancy test ^d	D	7.2.2.4.5	X					X		
Tumor evaluation(MRI or CT) ^e	D	7.2.1	X			X	X			X ^f
Pulmonary function tests, Chest CT ^g	D	7.2.2.5		Only to be done if clinically indicated						
Adverse events	D		X	Continuously					X	
Study Drug administration	D			X	X	X	X	X		

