7.2 Assessment types

7.2.1 Efficacy assessments

Tumor assessments are to be performed for screening purposes and are needed to determine the eligibility of the patient. Last available results of scans performed within 28 days prior to first dose of study drug will be used as baseline values. Negative scans at screening need not be repeated unless warranted by signs and symptoms suggesting disease progression. The assessment data will be collected until disease progression, unacceptable toxicity, death, protocol deviation or other reason that may leads to discontinuation or the end of study.

The following tumor assessments are to be performed and assessed prior to enrollment:

- Abdominal and pelvic triphasic CT or multiphase MRI;
- Chest X-ray (and/or chest CT if disease is present in chest).

To determine eligibility, measurable and non-measurable lesions must be assessed and target lesions identified prior to enrollment. For definition of measurable and target lesions please refer to RECIST 1.1 ([Appendix 1](#))

The same method of assessment and the same technique should be used to characterize each identified and reported lesion at baseline and after every 12 weeks while on-study. All radiology evaluations will be performed initially by the local radiologist.

Details of response assessment are provided in full protocol based on RECIST1.1, and are based exclusively on radiological findings obtained at tumor assessments.

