- d. A serum pregnancy test will be conducted locally at screening/baseline in all females of child-bearing potential, urine pregnancy test will be conducted at the end of treatment visit.
- e. Repeat scans (multiphase MRI or triphasic CT) at baseline and every 12 weeks thereafter. The same type of scan should be used at baseline and follow-up.
- f. Efficacy assessment will be collected until progression of disease (PD).
- g. If an investigator suspects a patient may be developing non-infectious pneumonitis, investigations such as pulmonary function tests, CT chest and referral to a pulmonologist should be considered.

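### Appendix 1 accepts best response PD only up to 12 weeks, but the first scan window runs to day 92, so where that rule is applied some on-schedule first-scan progression is classed as unknown

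*Protocol*

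**What the plan says.** Protocol section 7.2.1 tells the reader that "Details of response assessment are provided in full protocol based on RECIST1.1". The only place in either document that sets out how a best overall response is assigned is Appendix 1, section 14.1.17. It states that "The best overall response for a patient is always calculated, based on the sequence of overall lesion responses", and then lists the categories in order:

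- Stable disease: "SD = at least one SD assessment (or better) > 6 weeks after randomization/start of treatment (and not qualifying for CR or PR".
- Progressive disease: "PD = progression ≤ 12 weeks after randomization/ start of treatment (and not qualifying for CR, PR or SD".
- UNK takes everything else, that is, patients without a response and "without SD after more than 6 weeks or early progression within the first 12 weeks".

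The scan schedule comes from Protocol Table 7-1. The first post-baseline tumor evaluation is at "Visit 3 (week 12±1wk", with none at Visit 2. SAP Appendix 1 repeats the interval: "Repeat scans (multiphase MRI or triphasic CT) at baseline and every 12 weeks thereafter". Protocol section 7.1 adds that visits outside the windows "will not constitute protocol deviations".

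SAP 5.5.3 counts CR, PR, SD and PD using the investigator's best response. It has no UNK row and neither restates nor replaces the 12-week limit. SAP section 7 declares no change to the protocol's methods. Section 14.1.29 of the Appendix asks for study-specific choices to be recorded in the protocol or the analysis plan; neither document records one here.

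**The concern.** The 12-week limit belongs to a generic guideline. In this study it falls in the middle of the first scan window. A patient scanned on time in week 13, with clear progression, has no earlier post-baseline scan that could give SD and is too late for PD. The rule leaves only UNK, although progression has been documented.

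At stake is the PD percentage in the best-response table. Progressors moved to UNK no longer count as PD, and the SAP table has no row to show them. Two sites could also class the same patient differently, one recording PD and the other following the Appendix.

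**Working it through.** **Inputs.** Limit for PD: 12 weeks = 84 days (Protocol 14.1.17). First scan: week 12 ± 7 days (Protocol Table 7-1). Day numbering: first dose is day 1 (SAP 5.1.1). Duration formula in the Appendix: end − start + 1 (Protocol 14.1.34).

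**The plan's own figure.** SAP 5.1.1 places Visit n on day 12 × (n − 2) × 7 + 1. For Visit 3: 12 × 1 × 7 + 1 = 85, as the SAP table states.

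**Window.** 85 − 7 = 78 and 85 + 7 = 92, so days 78 to 92, which is 15 days.

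**Applying the rule to first-scan progression.** By elapsed days (study day − 1 ≤ 84), PD is possible through day 85. By the Appendix formula (study day ≤ 84), it is possible only through day 84. The table also tries a window centred on day 84.

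| Window | Day convention | Days classed UNK | Share of window |
|---|---|---|---|
| Days 78–92 | elapsed | 86–92 | 7/15 (47%) |
| Days 78–92 | end − start + 1 | 85–92 | 8/15 (53%) |
| Days 77–91 | elapsed | 86–91 | 6/15 (40%) |
| Days 77–91 | end − start + 1 | 85–91 | 7/15 (47%) |

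First-scan progression after day 85 is UNK under every convention. Under the Appendix's own formula the nominal week-12 visit on day 85 is lost as well.

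**Size, as an illustration.** Assume N = 60 (Protocol 10.8) and scan days spread evenly over days 78–92. Early progression is taken either from the PD rate in stratum 1 of the second phase II study (16/115) or from an exponential PFS curve, p = 1 − 0.5^(t/m), with t = 84/30.4375 = 2.76 months and median m from Protocol 1.2.1.2.

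| Source | Early progression | Of 60 | × 7/15 | × 8/15 |
|---|---|---|---|---|
| Phase II stratum 1, 16/115 | 13.9% | 8.3 | 3.9 | 4.5 |
| m = 9.7 months (phase II stratum 1) | 17.9% | 10.7 | 5.0 | 5.7 |
| m = 11.04 months (phase III, everolimus arm) | 15.9% | 9.5 | 4.5 | 5.1 |
| m = 16.7 months (phase II stratum 2) | 10.8% | 6.5 | 3.0 | 3.5 |

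The range is about 3 to 6 patients. Starting from 13.9% and keeping all 60 in the denominator, the PD percentage would fall to 13.9% × 8/15 = 7.4% (7 days lost) or 13.9% × 7/15 = 6.5% (8 days lost).

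**What does not move.** The overall lesion response at that scan is still PD, so under row 2 of SAP Table 2 it remains a PFS event on its own date. OS does not use it.

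**The case against.** The strongest reply is that SAP 5.5.3, the only analysis using best response, takes the investigator's determination and does not cite section 14.1.17. An investigator who sees progression on the first scan may simply record PD. Section 14.1.17 also opens with a general definition, the best response recorded from treatment start until progression, that has no time limit. The explicit pointer to Appendix 1 in section 7.2.1 concerns measurable and target lesions.

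Much of this stands. A reader might infer that the final table will show these patients as UNK. The documents do not support that, because the misclassification arises only where the Appendix rule is followed. The reply does not remove the problem, though. The SAP gives the investigator no alternative rule, the specific category rules follow the general definition in the same section, and SAP section 7 claims no departure from the protocol. The only stated rule gives the wrong category for an on-schedule scan.

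The size estimate is also open to challenge:

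- The phase II scan schedule is not in the documents.
- PFS events include deaths, which are not first-scan progression.
- Progression found on an unscheduled scan before week 12 is correctly PD.
- Phase II stratum 2, the source of the 16.7-month median, received octreotide LAR and reported no PD at all, so the true count could lie below the range.

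**Conclusion.** The rule is wrong as written for this schedule, and the consequence is small. Where section 14.1.17 is applied, first-scan progression on 7 or 8 of the 15 permitted days becomes UNK, and the PD percentage in a descriptive table can be understated. The figure of about 3 to 6 patients in 60 is an illustration; it depends on evenly spread scan days and on borrowed early-progression rates. Best response is not a named endpoint.

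A reader might go further and conclude that disease control is overstated. The documents do not support that. The SAP calculates no disease control rate, and neither PD nor UNK counts as control, so the numerator cannot change. The proportion would rise only if UNK patients were treated as missing and dropped under SAP 5.1. For example, with the phase II stratum 1 figures (11 PR + 78 SD = 89 of 115, or 77.4%, which is 46.4 of 60), dropping 3.9 patients would give 46.4/56.1 = 82.8%. No passage says that UNK is to be handled as missing, and section 14.1.17 allows such patients in the denominator.

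**What to change.** In SAP 5.5.3, record as a study-specific decision that best response is PD when the first post-baseline tumor assessment documents progression within the protocol scan window, through study day 92, and there is no prior CR, PR or qualifying SD. Give the limit as a day number: 13 weeks is 91 days, and under end − start + 1 a scan on day 92 would still fall outside it.

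The same paragraph should:

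- derive best response from the investigator overall lesion responses already recorded, since a SAP sentence cannot change best responses that sites have already entered;
- say how a first scan after day 92 showing progression is classed, because late visits are not deviations;
- add an UNK/not evaluable row and use the full FAS as denominator.

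SAP section 7 should list the change from the Appendix limit. The cost is a short SAP amendment and a small change to the derivation program. No new data are needed.
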